- Because trials on prevention of recurrent *S. aureus* infections have been disappointing, we will examine the efficacy of oropharyngeal *S. aureus* decolonization with 0.12% chlorhexidine gluconate (CHG) oral rinse, a widely available commercial product with an excellent safety profile.

Hypotheses

- Oral CHG rinse (0.12%) will be more effective than placebo at eradicating *S. aureus* oropharyngeal colonization after treatment completion.

Specific Aims

- To determine if CHG oral rinse can decolonize *S. aureus* oropharyngeal colonization better than placebo in children.

Study design

- Randomized, prospective, double-blind, placebo-controlled clinical trial of 0.12% CHG oral rinse vs. placebo oral rinse to decolonize the oropharynx among children.

Describe study population or sample material

- Subjects 5-17 years of age who have confirmed colonization of the oropharynx with *S. aureus* and who are able to gargle.

Sample size/power of primary endpoint

- The primary endpoint is eradication of *S. aureus* oropharyngeal colonization. To have 85% power to detect a 40% absolute difference in eradication between groups (10% for placebo and 50% for CHG), we will require 54 subjects total who complete the trial. We will need to screen potentially eligible children with rapid molecular tests for *S. aureus* oropharyngeal colonization to find eligible subjects. Estimating 25% of screened children will be eligible, and accounting for a 10% attrition rate, we will need to enroll 240 children for screening with the expectation that 60 will be eligible and participate and 54 will complete the clinical trial.

Assuming the project is successful, state the next step moving down the pathway to clinical applicability

- A randomized, prospective, multi-center, clinical trial of children of prevention of *S. aureus* skin infection that includes CHG oral rinses (in addition to body and nasal disinfectants) with a comparator group that will depend on standard of care at the time of development of the clinical trial protocol.

Hypothesis(es) and Aims (Do not exceed one page)

A. Hypothesis(es) to be Tested

Our primary hypothesis is 0.12% CHG oral rinse will be superior to placebo at eradicating *S. aureus* from the oropharynx of children age 5-17 colonized with *S. aureus* compared to placebo oral rinse.

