Subjects will also be swabbed for *S. aureus* and MRSA colonization at the anterior nares and oropharynx. Testing will be performed using two methods: direct microbiology cultures and rapid molecular testing. Microbiologic cultures will be performed by culturing swabs from sites taken to identify *S. aureus* and MRSA carriage will be transported to the research microbiology laboratory at LA BioMed at Harbor-UCLA and plated within 24 hours of collection. Swabs will be processed for *S. aureus* using blood agar and CHROMagar plates for rapid identification of *S. aureus* and MRSA. All *S. aureus* and MRSA isolates will be banked for pulse-field typing, determination of SCCmec type, and presence of the PVL locus (*lukF-PV* and *lukS-PV*). Rapid molecular testing will be performed using the GeneXpert MRSA/SA platform, which is currently available at our site.

Upon confirmation of eligibility, the study coordinators will call the pharmacy to randomize the participant and obtain the oral rinse. The randomization assignment list will be generated in advance by pharmacy. Randomization procedures by an assignment list will be prepared by a computer method. To ensure adequate balance of subjects between the CHG and placebo groups, treatment allocation will be assigned using a random number generation with randomization of blocks of four subjects each. The randomization list will be kept by the pharmacy and treatment allocation randomization will not be shared with either the study staff or patients. The research pharmacists will dispense the appropriate oral rinse to the participant and their parent/guardian. Placebo will be created using the inert vehicles components of CHG, as has been done previously.⁸⁹ Participants and their parent/guardian will be given detailed instructions on the use of the oral rinse both verbally and in a handout in either English or Spanish as preferred by the participant and their parent/guardian.

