Subjects randomized to oral CHG will be provided verbal and written instruction on use of CHG oral rinse. Subjects will be asked to use CHG oral rinse twice daily for 7 days. Subjects will be educated to rinse their mouth and gargle with CHG oral rinse for 60 seconds twice a day. Subjects will be instructed to use a watch or other timing device (e.g., smartphone) to ensure that at least 60 seconds have elapses. Research staff will demonstrate the technique for all subjects using drinking water. All subjects randomized to the CHG arm will be provided a new soft bristle toothbrush to prevent recontamination of the oropharynx with *S. aureus* from a contaminated toothbrush. Subjects randomized to usual care will not be provided with any of the above. Regardless of treatment allocation, study staff will educate all subjects' parent/guardian, and subject (if of sufficient age) with the clinical significance of the results of their positive test for oropharyngeal

S. aureus colonization. More specifically, they will be educated that currently testing for *S. aureus* oropharyngeal colonization is considered experimental and that if the test is positive, the clinical significance is unclear. They will also be educated that tens of millions, perhaps over 100 million Americans are colonized in the throat with *S. aureus*, and the vast majority do not suffer consequences of having this bacteria reside in the throat. Upon request, subjects will be provided with a written copy of their results as well as a written description of the clinical significance of oropharyngeal colonization that they can share with their provider, if they wish. All subjects, regardless of treatment allocation, will be provided written and verbal information about *S. aureus* and skin infection prevention and recognition of early disease. These materials were developed for previous studies done by our group.¹⁸

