Of note, we debated whether the control group not receiving CHG should receive no therapy or a placebo oral rinse. Obviously, placebo controlled trials are of stronger study design compared to non-placebo controlled studies. More specifically, in non-placebo studies, both patients and investigators will know the treatment allocation, which can lead to bias by both subjects and the investigative team. We did have concern that oral rinses/gargling with placebo or an inert substance may affect *S. aureus* colonization. However, a 1970 investigation examined this issue using quantitative techniques. Investigators asked subjects to gargle with saline and took serial quantitative cultures. They found that gargling specimens taken at 5 minute intervals for 25 minutes showed no significant decrease in organisms concentration, with mean organism concentrations at baseline of 7.11, 6.85 at 5 minutes, and 6.92 at 25 minutes.⁹⁰ This suggests that placebo will have no ability to decolonize oropharyngeal *S. aureus* from study participants.

At the baseline visit, study coordinators will also administer a pediatric *S. aureus* risk factor survey similar to surveys used for previous *S. aureus* and MRSA epidemiologic investigations by our group.^{9,17,18,76,80,84,85} Items from this survey have been based on careful reviews of the literature on *S. aureus* risk factors and have incorporated items used previously by the CDC, Health Departments, and other investigations examining MRSA risk.^{80,84} The baseline survey will collect information about demographics, medical history, antibiotic use, and behavioral risk factors for *S. aureus* infection and colonization. Participants and their parent/guardian will be given phone numbers of the study coordinator for questions. Participants and their parent/guardian will be compensated for their time for this and all study visits.

Follow-up visits

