Risks associated with study medication is believed to be minimal. Chlorhexidine-gluconate (CHG) oral rinse is an FDA-approved medication for the treatment of gingivitis. The known side effects of oral CHG oral rinse include staining of teeth and other oral surfaces, an increase in calculus formation; and an alteration in taste perception.¹⁰⁰ All of these potential side effects are transient, reversible, or preventable with education and standard oral hygienic practices (e.g., tooth brushing). All subjects will be educated on the proper use of the oral rinse. Subjects will be asked to report any adverse events to study personnel and to stop the use of the oral rinse if any severe side effects develop (swelling, pain, etc.). Staff will also be able to counsel subjects about the risks and benefits of the oral rinse to decolonize the oropharynx. Study personnel will also have cell phones, which subjects can call to ask questions about the study, use of the intervention oral rinse, and report adverse events. Subjects that report serious adverse events or other medical needs will be referred to the Harbor-UCLA Medical Centers' Pediatric Emergency Department.

An Investigational New Drug (IND) application will not be required, as a clinical investigation of a marketed drug is exempt from IND requirements if all of the criteria for an exemption in § 312.2(b) are met:

- The drug product is lawfully marketed in the United States.
- The investigation is not intended to be reported to FDA as a well-controlled study in support of a new indication and there is no intent to use it to support any other significant change in the labeling of the drug.
- In the case of a prescription drug, the investigation is not intended to support a significant change in the advertising for the drug.
- The investigation does not involve a route of administration, dose, patient population, or other factor that significantly increases the risk (or decreases the acceptability of the risk) associated with the use of the drug product (21 CFR 312.2(b)(1)(iii)).
- The investigation is conducted in compliance with the requirements for review by an IRB (21 CFR part 56) and with the requirements for informed consent (21 CFR part 50).
- The investigation is conducted in compliance with the requirements of § 312.7 (i.e., the investigation is not intended to promote or commercialize the drug product).

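### A toothbrush issued only to the CHG arm bundles a second measure with the rinse and could reveal the arm

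*Combined protocol and SAP*

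**What the plan says.** The Structured Abstract (Study design) describes a "Randomized, prospective, double-blind, placebo-controlled clinical trial of 0.12% CHG oral rinse vs. placebo oral rinse". The Baseline visit section keeps the randomization list in the pharmacy and says that "treatment allocation randomization will not be shared with either the study staff or patients". The same section explains why a placebo was preferred to an untreated control: "in non-placebo studies, both patients and investigators will know the treatment allocation, which can lead to bias by both subjects and the investigative team".

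Between those statements, the Baseline visit section also says: "All subjects randomized to the CHG arm will be provided a new soft bristle toothbrush to prevent recontamination of the oropharynx". The source of recontamination it names is a contaminated toothbrush. The next sentence reads: "Subjects randomized to usual care will not be provided with any of the above". No other section mentions a toothbrush supply, and no design statement contains a usual-care arm.

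The wording on rinse instructions is mixed. One sentence is restricted to an arm: "Subjects randomized to oral CHG will be provided verbal and written instruction on use of CHG oral rinse". The Human Subjects section likewise promises extra information on the CHG rinse to those in the intervention group. Elsewhere the wording is general: "Participants and their parent/guardian will be given detailed instructions on the use of the oral rinse both verbally and in a handout", and in the Human Subjects section, "All subjects will be educated on the proper use of the oral rinse". The Baseline visit section also has staff show the technique with water to every child.

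**The concern.** There are two separate problems.

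The first is a co-intervention. The toothbrush is supplied to keep the oropharynx from being recolonized, and the oropharynx is where the primary outcome is measured. The primary hypothesis concerns the CHG rinse against placebo rinse. If only one arm receives the toothbrush, the contrast no longer isolates the rinse. The Limitations section argues that adding other decolonizing agents would stop the trial from determining what the rinse does. A toothbrush is not such an agent, but the same reasoning applies to it.

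The second is the blind. An item supplied by arm is a visible marker of the arm. Aim 2 surveys side effects, tolerability and adherence in both groups, largely at Visit 2, and adverse-event percentages are tested between groups. Those answers depend on what families and staff believe about the treatment. The Human Subjects section also lists tooth brushing among the measures that can prevent the rinse's side effects, so the toothbrush could bear on the adverse-event comparison even with the blind intact.

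**Working it through.** **1. Group sizes.** The Power and Sample Size section gives 27 per group for 50% versus 10%, alpha 0.05 and 85% power. Two-sidedness is assumed here, as the plan does not state it. The figure reproduces:

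- Uncorrected: n = [1.960·√(2·0.30·0.70) + 1.036·√(0.50·0.50 + 0.10·0.90)]² / 0.40² = (1.270 + 0.604)² / 0.16 ≈ 21.96, so 22.
- With continuity correction: (21.96/4)·[1 + √(1 + 4/(21.96·0.40))]² ≈ 26.7, so 27.
- After attrition: 54/(1 − 0.10) = 60 randomized, 30 per arm. Aim 3 also assumes 30 in the CHG arm.

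None of these figures is disputed, and none changes with the fix.

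**2. What the rule produces if followed.**

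| | Toothbrush | No toothbrush |
|---|---|---|
| CHG | 30 | 0 |
| Placebo | 0 | 30 |

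Among the planned completers the cells are 27, 0, 0 and 27. These counts restate the rule. They do not measure bias.

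**3. What the primary comparison then estimates.** Write c for the effect of CHG on the probability of eradication at day 7, t for the effect of a new toothbrush, and i for any interaction.

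- Expected difference, CHG minus placebo = c + t + i.
- With both off-diagonal cells empty, the data determine only this sum. No covariate adjustment or model can recover c.
- The document gives no value for t. It may be zero. The plan's only statement is the purpose for which the toothbrush is supplied.

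**4. When the arm would be revealed.** Three conditions must hold: the rule is followed, the person knows it, and the person sees the toothbrush or learns that none was given.

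- *Study staff.* If they hand out the toothbrush, someone must tell them the arm, which the concealment rule forbids. If the pharmacy hands it out with the rinse, staff are shielded at that moment, but they know the protocol and could learn of it at a visit or telephone call.
- *Families.* Each sees only its own child's supplies. The available text does not say that families are told the rule.
- *Who hands it over.* The document does not say.

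**5. Which outcomes are exposed.** Eradication is read from swabs tested in a laboratory, so expectation has limited room to act on it. The co-intervention can still act on it. Adherence, tolerability and adverse events are reported by participants and parents, so knowledge of the arm matters most there.

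**The case against.** The strongest reply is that this is leftover drafting. The Baseline visit section records that the team debated giving the control group no therapy or a placebo rinse. The usual-care sentence fits the rejected option, and the neighbouring toothbrush sentence may come from the same text. The usual-care sentence also clashes with the demonstration promised to every child just before it. This is plausible for the usual-care sentence. It is less convincing for the toothbrush sentence, which is explicit and carries its own rationale. Both are current text, and a site following them would supply toothbrushes by arm.

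A second reply is that the pharmacy could dispense the toothbrush and that the primary outcome is microbiological. Both points reduce the threat from unblinding. Neither removes the co-intervention, and the second does not protect Aim 2.

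A reader might also infer that placebo children get no rinse instructions or follow a different regimen. The documents do not support that. The general instruction and education statements and the demonstration for all children point to a common regimen, so the arm-specific instruction wording needs only tidying.

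**Conclusion.** The point stands as an internal inconsistency that should be corrected. As written, the toothbrush goes to the CHG arm only and coincides completely with CHG. The day-7 comparison would therefore estimate rinse plus toothbrush, and the arm could be revealed to anyone who knows the rule and sees the item.

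This rests on two assumptions: that the rule is carried out, and that placebo children receive no toothbrush. The second is an inference, because the sentence withholding the items names usual care rather than placebo, but nothing in the document supplies placebo children with one.

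Two stronger conclusions might be drawn and should not be. One is that the blind would certainly be broken. The documents do not say who hands over or later sees the toothbrush, so unblinding is a risk and not an established fact. The other is that a positive eradication result would be due to the toothbrush. No toothbrush effect is given, so neither the size of any bias nor whether it is more than trivial can be derived. Confidence is high about what the text says and does not extend to the size of the consequences.

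**What to change.** - Give the same new toothbrush to both arms, or to neither. If both receive it, the comparison estimates the rinse effect among children who have a new toothbrush. If neither does, it estimates the rinse effect with no added item.
- Delete the usual-care sentence.
- As a wording clean-up in the Baseline visit and Human Subjects sections, refer to the study oral rinse wherever instructions now name CHG. Address them to all randomized children, and state that the instructions, handout and demonstration are identical in both arms (60 seconds, twice daily, 7 days).

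The cost is a wording amendment, one common handout, and about 30 further toothbrushes at most. There are no added visits or staff, and the sample size does not change.

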Our primary outcome is *S. aureus* eradication at 7 days (test of cure (TOC)). Secondary outcome is eradication at 1 month (long term follow up). Study staff will administer surveys to subjects and/or their parents about risk factors hypothesized to predict treatment success. Secondary outcomes include safety, tolerability, and adherence to oral CHG. We will also examine predictors of eradication, including pathogen level factors. Pathogen-level factors will be examined using *S. aureus* whole genome sequencing, which will allow us to quantify the presence or acquisition of the *qacA/B* gene, which is associated with CHG resistance. WGS will also allow us determine if stains associated with persistence after CHG use represent pre-existing colonizing strains or acquisition of new strains.

If CHG oral rinse is efficacious at eradication, our findings will form the foundation for a larger, more comprehensive intervention to prevent recurrent SSTIs in children. If CHG oral rinse cannot decolonize the oropharynx, then investigations may need to focus on other strategies to prevent *S. aureus* disease. Regardless of results, our trial will forward the field of prevention of this extremely common and potentially deadly infection.

Structured Abstract (Do not exceed one page)

Describe the medical problem as it relates to children

- Community-associated (CA) *Staphylococcus aureus*, including methicillin-resistant *S. aureus* (MRSA), is the most commonly identified cause of skin and soft tissue infections (SSTIs) and affects children disproportionately.

State the incidence/prevalence of problem in children

- Four in 100 children in the U.S. will experience a SSTI annually, resulting in over one million infections annually, a problem further complicated in that over 50% of children who have a *S. aureus* skin infection will develop a recurrent infection.

Background that will lead to the research gap (*may use 2 sentences*)

- Our group found that, despite common belief, the most common site of colonization of *S. aureus* on the human body is not the anterior nares (nose), but the oropharynx. There are mounting data that decolonization regimens that do not eradicate oropharyngeal colonization are ineffective at preventing recurrent *S. aureus* SSTIs.

State the primary research gap this study will address

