Participants will be asked to come to the research clinic 7 days after initiation of oral CHG, i.e., at the end of their treatment (Visit 2). A subsequent visit will occur at 28 days (Visit 3). The purpose of these visits is to ascertain oropharyngeal eradication of *S. aureus* both short term (primary study outcome) and longer term. Based on previous investigations conducted at our center(s), we estimate a 10% attrition rate.^{75,77,78,81,82} At Visit 2, participants will be swabbed the nares and oropharynx for the presence of *S. aureus* and to complete a follow-up survey about any recurrent infections, new medical history, or receipt of antibiotics. At Visit 3, participants will return to the research clinic to complete a follow-up survey. Study staff will also call all subjects remind them of their upcoming study appointments and at days 14 and 21 to address any questions the participant or their parent/guardian may have about the study. Adverse events will be measured at each scheduled and unscheduled (see below) follow-up visits. Adverse events will be measured using the Medical Dictionary for Regulatory Activities Terminology (MedDRA) version 14.0 or later terms.

Unscheduled visits

If participants or their parent/guardian experience potential adverse drug events that occur during the follow up period, subjects or their parent/guardian will be encouraged to contact study staff. If the event may be of clinical concern, the event will be referred to a study physician and the oral rinse discontinued, if applicable. If deemed necessary by the study physician or the subjects' primary physician, participants will be asked to return to the research clinic for evaluation by a study investigator.

Aim 1: Determine the efficacy of oropharyngeal decolonization among children suffering from CA-MRSA and other *S. aureus* skin infections

To determine if oropharyngeal *S. aureus* colonization can be eradicated, we will perform a prospective, double blind randomized controlled clinical trial of 0.12% oral chlorhexidine (CHG) oral rinse versus placebo for children age 5-17 with *S. aureus* oropharyngeal colonization. We hypothesize that 0.12% CHG rinse will

reduce oral *S. aureus* colonization better than placebo treatment. The findings from this Aim will provide “proof of principle” data on the ability of oral antiseptics to eradicate oropharyngeal *S. aureus* colonization in children.

Power and Sample Size

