WGS sequencing will addresses several hypothesis in those subjects randomized to CHG oral rinses, specifically: a) strains that are found in the oropharynx at end of treatment (Day 7) will be identical genetically to those at baseline and not represent acquisition of new *S. aureus* strain; b) recolonizing *S. aureus* strains at Day 28 among subjects successfully eradicated at Day 7 will represent (re)colonization with the original isolate that colonized the nasopharynx from the same individual (if present at baseline) or a new *S. aureus* strain not present at baseline and; c) nasal isolates found at baseline and follow up will be identical to synchronously identified oropharyngeal *S. aureus* isolates.

Based on data in older adults,¹⁹ we estimate that of the 30 subjects randomized to the CHG arm, 50% will be decolonized, leaving 15 subjects who will be *S. aureus* positive at the oropharynx at the end of treatment. Based on data of recolonization after decolonization in which recolonization can occur after the decolonization regimen is completed,¹⁰ we estimate that a 10% increase in colonization will be seen at Day 28, i.e., 18 subjects will be oropharyngeally colonized with *S. aureus* at Day 28. Thus, we anticipate we will have results in 33 pairs of oropharynx isolates (15 between baseline and Day 7, and 18 between baseline and Day 28, for a total of 66 isolates total). Additionally we will conduct whole genome sequencing on baseline nasal *S. aureus* isolates associated with the subsequent oropharynx isolates identified at Day 7 and/or Day 28. Based on previous data suggesting that ~45% of those colonized at the oropharynx will be colonized at the anterior nares,^{18,46,95} we estimate an additional 30 (45% x 66) nasal *S. aureus* isolates from baseline and follow-up will be present synchronously with oropharyngeal isolates.

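### The Day 7 primary swab has no stated gap after the last rinse, no neutralizing step and no named assay, so carry-over of antiseptic in the CHG arm alone cannot be excluded

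*Combined protocol and SAP*

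**What the plan says.** - **Endpoint.** The Scientific Abstract gives the primary outcome as "eradication at 7 days (test of cure (TOC")), followed by "Secondary outcome is eradication at 1 month (long term follow up").
- **Hypothesis.** The Structured Abstract frames the effect as eradicating "oropharyngeal colonization after treatment completion".
- **Timing.** The Follow-up visits section puts the visit "7 days after initiation of oral CHG, i.e., at the end of their treatment (Visit 2"). Aim 3 uses the same equation, referring to strains "found in the oropharynx at end of treatment (Day 7").
- **Regimen.** The Baseline visit section states: "Subjects will be asked to use CHG oral rinse twice daily for 7 days".
- **Comparator.** The same section states: "Placebo will be created using the inert vehicles components of CHG".
- **Sampling.** Follow-up visits: "At Visit 2, participants will be swabbed the nares and oropharynx for the presence of" *S. aureus*. Culture and rapid molecular testing are both described for baseline. Neither is named as the test that decides eradication at Day 7.
- **Visit 3.** Follow-up visits mentions only a survey at this visit. The Human Subjects section has nares and oropharynx swabs at Visits 1, 2 and 3.

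No section states a minimum interval between last rinse and swab, a record of the time of the last rinse, or a neutralizing step.

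**The concern.** A test of cure asks whether the organism has gone once treatment has stopped. Here the swab coincides with the end of treatment. If antiseptic left in the throat is picked up on the swab and inhibits growth in the laboratory, a child who is still colonized can be recorded as eradicated. Placebo is vehicle only, so this error could arise in one arm only. Neither randomization nor blinding removes it, because it follows from the content of the active rinse.

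At stake is the meaning of the single confirmatory test. The protocol intends a positive result to support a larger prevention trial. That trial would rest on weaker ground if part of the Day 7 difference came from the specimen and not from the child's throat.

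**Working it through.** **1. When the last rinse falls.** Two rinses a day for 7 days is 2 × 7 = 14 uses. If the first is taken on the evening of the baseline day, the fourteenth falls on the morning of Visit 2. If the first is taken that morning, the fourteenth falls on the evening before Visit 2. The plan allows either, so the interval may be a few hours or overnight.

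**2. The plan's own sample size.** Inputs from Power and Sample Size: 50% versus 10%, alpha 0.05, power 85%.
- Uncorrected two-sided normal formula, mean rate 0.30: n = [1.96·√(2·0.30·0.70) + 1.036·√(0.50·0.50 + 0.10·0.90)]² / 0.40² = 21.96, so 22 per arm.
- With continuity correction: (21.96/4)·[1 + √(1 + 4/(21.96·0.40))]² = 26.7, so 27 per arm and 54 in total, as stated.
- 54 / 0.90 = 60 randomized, as stated.
- Exact Fisher power at 27 per arm is 87%.

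The sample size is not in question.

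**3. Illustrative model of carry-over.** Let *t* be true eradication in the CHG arm and *m* the share of still-colonized CHG children whose swab is falsely negative. The observed CHG rate is *t* + (1 − *t*)·*m*; the placebo rate is unaffected. The values of *m* are assumptions, since the documents give none. The test is Fisher's exact at 0.05, as in the Data Analyses section. Its sidedness is not stated and is taken as two-sided. Probabilities come from full enumeration at 27 per arm.

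*No true effect (same true rate in both arms):*

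| m | Observed CHG rate, true 10% | Chance of p<0.05 | Observed CHG rate, true 30% | Chance of p<0.05 |
|---|---|---|---|---|
| 0% | 10% | 0.7% | 30% | 2.5% |
| 10% | 19% | 6% | 37% | 5% |
| 20% | 28% | 25% | 44% | 12% |
| 30% | 37% | 54% | 51% | 25% |

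The *m* = 0 row is the test's actual type I error, which lies below 5% because Fisher's test is conservative.

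**4. Two reference points.**
- For carry-over alone to produce the whole planned contrast, *m* would have to be (0.50 − 0.10)/0.90 = 44%.
- With 3/27 negative on placebo, 11/27 on CHG gives p = 0.028 and 10/27 gives p = 0.054. Near the boundary, one false negative changes the result.

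**5. If the planned effect is real.** With *t* = 50% and *m* = 10%, 20% or 30%, the observed CHG rate is 55%, 60% or 65%. Against 10% on placebo, the true 40-point difference is then reported as 45, 50 or 55 points.

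**The case against.** **The mechanism and its size are not in the documents.** Nothing there says how long CHG persists in the throat or whether it inhibits a swab culture. The gargling study cited in the Baseline visit section used saline, so it speaks to a placebo effect and not to residual CHG. This stands: a reader might infer that a positive Day 7 result would be an artefact, and the documents do not support that. They support only that the plan does not exclude it.

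**Silence is not proof of absence.** The Visit 2 survey covers adherence, and neither that instrument nor a laboratory manual is in the documents. It is fair to say that rinse timing and neutralization are not stated, but not that they will not be done.

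**Culture may not be the deciding assay.** If the molecular test decides, inhibition of growth does not apply in the same form. This stands, and it makes the concern conditional. It is also a reason to name the assay.

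**Short-term suppression is a real drug effect.** Follow-up visits openly calls Day 7 the short-term outcome, and the study is presented as proof of principle. Suppression in the throat is legitimately part of such an endpoint; antiseptic inhibiting growth on the swab is not. The table concerns only the second.

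**Day 28 and sequencing limit misreading.** Sustained decolonization is a secondary hypothesis, and Aim 3 compares breakthrough strains with baseline strains. Both help interpretation, but neither changes the primary p-value. A reader might infer that only a child also negative at Day 28 should count as eradicated. That goes too far, because Aim 3 expects some Day 28 positives to be newly acquired strains, and the rule would score those as failures of the rinse.

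**Conclusion.** The concern holds as a gap in the specification of the primary endpoint. Followed as written, the plan permits a measurement error that could occur only in the CHG arm and would favour CHG. Whether it would occur, and how often, cannot be learned from the documents.

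The probabilities above are illustrations. They rest on culture deciding the endpoint, the assumed values of *m*, no misclassification on placebo, a two-sided test and 27 completers per arm. Within that range, 10% carry-over does little harm: the false-positive chance is about 5% to 6%, near the nominal level. At 20% to 30% it reaches 12% to 25% if true eradication is 30% in both arms, and 25% to 54% if it is 10%. The correction is worth making before enrolment because it is cheap and removes the doubt.

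**What to change.** In Follow-up visits:
1. State a fixed minimum interval between the last rinse and the Visit 2 throat swab, achieved through the timing of the swab, with the rinse regimen unchanged.
2. Record the time of the last rinse in both arms.
3. Collect the swab in a medium that neutralizes antiseptic.
4. Name the assay that decides eradication.

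In the outcome definition and the analysis section:

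5. Describe a Day 7 negative as end-of-treatment clearance and report it beside the Day 28 result. Use the planned sequencing to separate return of the original strain from a new one. Do not make a negative Day 28 swab a condition for eradication.
6. Reconcile Follow-up visits (survey only at Visit 3) with the Human Subjects section (swabs at Visits 1, 2 and 3), since the Day 28 result depends on that swab.

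The cost is slightly tighter visit scheduling, one data field and a neutralizing medium for about 60 swabs. Arms and sample size do not change.
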